9.2 Integrated Correlative Studies

- 9.2.1 Quantification/Characterization of CD27+ cells in the Tumor Microenvironment by Immunohistochemistry (IHC)
- 9.2.1.1 Collection of Specimen(s): FFPE tumor tissue
- 9.2.1.2 Handling and Shipping of Specimen(s): FFPE tumor blocks are preferred.
 Alternatively, a minimum of 13 unstained glass slides with 4-micron thick sections from FFPE per collection timepoint are acceptable. Please include a copy of the deidentified surgical pathology report, as well as study, site and patient study numbers. All FFPE specimens for correlative studies may be shipped together.

Shipping Procedure:

- 1. Place the block or slides in small zip-lock bag and seal.
- 2. Insert the bag containing the block or the slides in a bubble wrap bag.
- 3. Place wrapped samples inside the largest compartment of specimen biohazard bag and seal.
- 4. Insert a copy of the de-identified surgical pathology report in the outer pocket of the specimen biohazard bag.
- 5. Include a refrigerated cold pack (not frozen) if shipping in the summer months.
- 6. Place the specimen biohazard bag into the box and close.
- 7. Complete the transport documents and place into waybill pouch; affix to box.
- 8. Ship package to Mayo Clinic at the address below.
- 9. Please send email on the day of the shipment.

Please send FFPE tissue to:

Predolin Biobank Attn: [name] Mayo Clinic [name]

- Methodology: The integrated biomarker (CD27 IHC) assay will be performed on 9.2.1.3 formalin-fixed paraffin-embedded (FFPE) tissue. Biopsies should be obtained under radiologic or other guidance, as appropriate, per institutional procedures. Tissues should be placed in preservative no later than 30 minutes following removal from the body (ideally with 5-10 minutes). If tissue is obtained via core biopsy, a minimum of 3 and up to 6 cores are requested; however, less than the goal amount of tissue is acceptable, and should be based upon the clinical judgment of the clinician performing the procedure. Based upon prior studies, it is feasible for up to 6 to 8 core biopsies to be obtained depending on the site being sampled, the size of the mass, and the safety of the procedure. Specimens should then be fixed using 10% Neutral Buffered formalin for 20 ± -4 hours and then processed into FFPEs. If fixed specimens cannot be processed into FFPE within the period specified above, transfer the specimen to a container of 70% histology-grade alcohol where the specimen can be stable for up to 2 weeks. If the site cannot process tissue into FFPE, then ship specimens in 70% alcohol. Tissue blocks should be ideally released for the biomarker study. In the event this is not possible, serial 4 µm sections should be obtained from each core and mounted on positively-charged unstained glass slides. A total of 3 slides created from biopsy obtained at the time of registration should be forwarded from the Predolin Biobank to Mosaic Laboratories. A repeat biopsy is mandatory for patients who wish to cross-over from Group 1 to Group 2 in the event of progression. Three additional slides obtained at the time of progression should be forwarded from the Predolin Biobank to Mosaic Laboratories for these patients. Additional glass slides will be created for exploratory correlative studies as specified on section 9.1 (Specimen Requirements for Correlative Studies).
- 9.2.1.4 Statistical Analysis: We will use the "marker-by-treatment predictiveness curves" in Janes et al. to explore CD27 as a potential predictive biomarker for the benefit of Varlilumab. Specifically, we will display the response rate as a function of the percentiles of CD27 for each treatment arm: Varlilumab plus Nivolumab and Nivolumab alone. We will use logistic regression to model the response rate as a function of treatment and CD27 (as a continuous variable). The distribution of CD27 will be estimated empirically in the entire trial population and used to calculate CD27 values corresponding to each fixed percentile. If the two predictiveness curves cross (suggesting predictive potential of CD27), the point where the two curves cross would be a possible choice of threshold for dichotomizing CD27 into "low" versus "high". Threshold levels shown to be best predictors of clinical outcomes will be considered as reference for later pivotal trials.

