2.4 Correlative Studies Background

- 2.4.1 Integrated Biomarkers
- 2.4.1.1 Quantification and Characterization of CD27+ Cells in the Tumor Microenvironment by Immunohistochemistry (IHC)

The costimulatory molecule CD27 is a member of the tumor necrosis factor (TNF) receptor superfamily, and is constitutively expressed on the majority of mature T-cells, memory B cells, and a portion of natural killer cells. The interaction of CD27 with its ligand (CD70) plays key roles in activation, proliferation and survival processes of different immune cells. CD27 expression is also present on most B-cell malignancies at varying levels. It is therefore postulated that CDX-1127 (varilumab) - an agonist anti-CD27 monoclonal antibody – may exert its anti-tumor activity through activation of CD27-expressing T-cells in the context of T cell receptor stimulation and also through direct cytotoxic activity on tumor cells expressing CD27.

We therefore hypothesize that the expression of CD27 in the tumor cells and/or on its surrounding microenvironment is required for CDX-1127's (varlilumab's) antitumoral activity. We further hypothesize that the level of expression of CD27 along with its localization (tumor cells vs. immune cells) may serve as a predictive biomarker for the activity of CDX-1127 (varlilumab) in patients with B-cell lymphomas. To test this hypothesis we will assess CD27 expression level and localization by IHC on tumor biopsies obtained at the time of registration from patients treated under this protocol. CD27 expression will not be required for participation in the study (integral biomarker). The level of CD27 expression along with its localization (tumor cells vs. immune cells) will be compared between patients who achieve clinical benefit from treatment with CDX-1127 (varlilumab). For patients in group 1 (nivolumab single-agent) who agree to undergo a repeat biopsy to confirm progression of disease and then cross over to group 2 (combinatory therapy with CDX-1127 (varlilumab) and nivolumab), the CD27 IHC assay will be repeated and compared to baseline.

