The CD27 expression evaluation via IHC will be performed centrally by Mosaic Laboratories, L.L.C. ([name]) using a proprietary assay using the rabbit mAb clone EPR8569 from Abcam. CD27 staining will be evaluated by image analysis using an Aperio image analysis algorithm and the final score will be expressed as % of cells at 0 (unstained), 1+, 2+ and 3+, in addition to number of CD27+ cells/mm2. Validation report can be provided upon request.

- 2.4.2 Exploratory Biomarkers
- 2.4.2.1 Comprehensive Analysis of Immune Cell Subpopulations using Mass Cytometry (CyTOF)

CyTOF (cytometry at time-of-flight) or mass cytometry is a new single-cell proteomics platform that uses mass spectrometry to evaluate more than 45 simultaneous parameters on a single-cell level (Bendall *et al.*, 2012). This technology uses nonradioactive non-biological isotopes as reporters tagged to antibodies. Measurements are based on mass spectrometry, which largely avoids the hurdles of interference and spectral overlap seen with standard fluorescence-based flow cytometry. CyTOF is an ideal platform for the study of the tumor microenvironment given its ability to assess a large number of simultaneous parameters and resolve small differences in a heterogeneous population of cells. Taking advantage of the simultaneous assessment of several parameters per cell, CyTOF retains the ability to quantitate main lineage subsets in samples as small as 100,000 cells (Yao *et al.*, 2015). This is particularly useful in situations where cell count is limited - such as tumor biopsies - or in the assessment of rare immune cell subsets.

CyTOF is therefore a powerful tool to study a complex biological system such as the microenvironment of B-cell lymphomas, especially in the context of a study using immune modulating drugs. Since both Nivolumab and CDX-1127 (varlilumab) may have a broad range of effects on different populations of cells – including tumor cells and host immune cells – an assay that simultaneously characterize these effects is necessary. The CyTOF assays will be performed on two different specimen types: (1) single-cell suspensions created from tumor samples obtained at the time of registration and at the time of treatment cross over (for patients in group 1) and on (2) peripheral blood mononuclear cells (PBMC) obtained before the infusion of the study drugs during the first 24 weeks of treatment.

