9. BIOMARKER, CORRELATIVE, AND SPECIAL STUDIES

9.1 Specimen Requirements for Correlative Studies

In this study, we propose several correlative studies, as detailed below. These assays are

specifically chosen to provide information on the status of the immune system in general as well as specific information related to the mechanism of action of the study drugs. One integrated biomarker study (CD27 by IHC) has been included which has been approved by the Biomarker Review Committee (BRC) of the Cancer Therapy Evaluation Program (CTEP). All other correlative studies will be exploratory in nature. Although exploratory, the proposed studies will be done on specimens obtained at time points relevant to standard clinical practice (prior to treatment, and at the time of suspected progression) in order to avoid unnecessary risks. The scientific information obtained from these studies is intended to be hypothesis-generating and will help us advance our understanding of the anti-tumoral immune system in the context of simultaneous manipulations using immunomodulatory drugs in lymphoma.

Submission of tumor tissue obtained from a biopsy performed within 60 days of registration is a mandatory part of this protocol. This tissue will be used to confirm the diagnosis and correctly stratify patients between categories A or B (Section 3.1.1). Submission of tumor tissue obtained from a biopsy performed to at the time of suspected disease progression is optional, except for Group 1 patients who cross over to Group 2, for these patients, the biopsy is mandatory. The importance of a repeat biopsy for patients in Group 1 who are suspected to have progressive disease is explained by the fact that responses to immunotherapy drugs may differ from those of standard cytotoxic treatments. Before proceeding with additional therapy we must exclude pseudo-progression and delayed responses by obtaining a repeat biopsy.

The biopsies obtained at the time of progression for patients in Group 2 or for those in Group 1 not wishing to cross-over to Group 2 are exploratory in nature. We anticipate that these biopsies will be done in approximately 25% of patients (some for this study and some also for eligibility in subsequent trials). Even though the cohort may be small, we may potentially gain insights into whether patients progress despite increased immune cell infiltration into the tumor.

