13.5 Analysis of Exploratory Endpoints

To determine the effect of combination therapy with CDX-1127 (varlilumab) and nivolumab on the immune system as assessed by immunohistochemistry (IHC), mass cytometry (CyTOF) and changes in serum cytokine profile, multiple measures will be evaluated. For each measure below, baseline values and changes in these parameters over time will be both graphically and quantitatively summarized and explored. Standard paired comparisons methodologies (Wilcoxon signed rank and McNemar's tests) will be used to assess changes in these variables before and after therapy. In addition, baseline values and changes over time in each measure will be explored in relation to clinical outcome. Differences between responders and non-responders will be assessed using Wilcoxon's rank sum (continuous data) or Fisher's exact (categorical data) test. The relationship between each measure and time to event measures (PFS, OS) will be evaluated using Cox's proportional hazards models and log-rank tests.

CD27 IHC: CD27 expression will be evaluated in terms of level (an ordinal • variable such as low, medium, high), % of cells expressing, and location (expression in tumor cells vs. expression in normal immune cells). The expression level can be gathered continuously and may also be evaluated as a categorical variable (low, medium, high expression for example). These values will be evaluated as predictors of response. This is the only integrated biomarker. The expression level of CD27 will be analyzed using the "marker-by-treatment predictiveness curves" in Janes et al. to explore CD27 as a potential predictive biomarker for the benefit of Varlilumab. Specifically, we will display the response rate as a function of the percentiles of CD27 for each treatment arm: Varlilumab plus Nivolumab and Nivolumab alone. We will use logistic regression to model the response rate as a function of treatment and CD27 (as a continuous variable). The distribution of CD27 will be estimated empirically in the entire trial population and used to calculate CD27 values corresponding to each fixed percentile. If the two predictiveness curves cross (suggesting predictive potential of CD27), the point where the two curves cross would be a possible choice of threshold for dichotomizing CD27 into "low" versus "high". Threshold levels

shown to be best predictors of clinical outcomes will be considered as reference for later pivotal trials.

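### CD27 predictiveness curves: crossing of the fitted curves is taken to suggest prediction and to offer a cut-off, with no interaction estimate and no measure of uncertainty

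*Combined protocol and SAP*

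**What the plan says.** Section 2.4.1.1 states the hypothesis: the level and location of CD27 expression "may serve as a predictive biomarker for the activity of CDX-1127 (varlilumab) in patients with B-cell lymphomas". Section 9.2.1.4, repeated almost word for word under CD27 IHC in 13.5, gives the analysis. The model is described so: "We will use logistic regression to model the response rate as a function of treatment and CD27 (as a continuous variable". Response rate is displayed against CD27 percentile for each arm, and the reading rule follows: "If the two predictiveness curves cross (suggesting predictive potential of CD27), the point where the two curves cross would be a possible choice". The choice meant is that of a cut-off to split CD27 into low and high. The paragraph ends: "Threshold levels shown to be best predictors of clinical outcomes will be considered as reference for later pivotal trials".

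Neither section mentions a treatment-by-CD27 estimate, a band for the curves, or an interval for the crossing point. The other tests that 13.5 lists for every measure (signed rank, McNemar, rank sum, Fisher, Cox, log-rank) address change over time or association with outcome. None asks whether the treatment effect varies with CD27.

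On status, 13.5 says of CD27: "These values will be evaluated as predictors of response. This is the only integrated biomarker". Section 9.1 introduces this one integrated study and then says: "All other correlative studies will be exploratory in nature". Its later sentence, "The scientific information obtained from these studies is intended to be hypothesis-generating", therefore does not clearly cover CD27, although 13.5 lists CD27 under exploratory endpoints.

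**The concern.** A marker is predictive when the treatment effect changes with its value. Whether two fitted curves happen to cross inside the data is an indirect sign of that. Two lines estimated from 48 patients each will rarely be parallel, so they often cross by chance. The smaller the overall treatment effect, the closer together the curves lie and the more often this happens. Chance crossing is therefore most frequent when the combination adds nothing overall, which is when a crossing could be read as a subgroup that benefits. Conversely, CD27 can be predictive without any crossing, if the benefit grows with CD27 but never changes sign. The plan does not say that non-crossing means CD27 is not predictive, but it offers no other criterion.

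What is at stake is a cut-off reported without its uncertainty from the trial's only integrated biomarker, in a plan that considers such thresholds for pivotal trials. The primary endpoint, the interim rule and safety monitoring are not affected.

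**Working it through.** **Inputs.** From 13.1.3: 48 evaluable patients per group, 1:1 allocation, response 25% v 45%, one-sided 0.15. Assumptions: smaller (25% v 35%) and null (25% v 25%) effects, CD27 available for all 96 patients, and the CD27 distribution. The assay scales in 2.4.1.1 ("the final score will be expressed as % of cells at 0 (unstained), 1+, 2+ and 3+, in addition to number of CD27+ cells/mm2") suggested five shapes: normal; uniform, beta(1,4) and beta(4,1) percentages; and a lognormal density with log-SD 1. Each is scaled to SD 1.

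**The plan's own figure.** The CD27 analysis has none. For the primary comparison, exact enumeration of the one-sided Fisher test at 0.15 with 48 per group gives 80.9% power against the stated 80%, so the design inputs reproduce.

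**Model.** With T = 1 for the combination and M = CD27:

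logit p = b0 + bT·T + bM·M + bTM·T·M, and the curves cross at M* = -bT / bTM.

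With treatment and CD27 as main effects only, the curves are parallel on the logit scale and cannot cross. The planned use therefore implies the product term, and adding it is only a clarification of wording.

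**No true interaction** (4,000 trials per scenario; CD27 prognostic log-odds 0 or 0.5 per SD; ranges over shapes):

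| True response rates | Cross, observed CD27 range | Cross, 10th-90th percentile |
|---|---|---|
| 25% v 45% | 30-48% | 15-23% |
| 25% v 35% | 53-67% | 35-46% |
| 25% v 25% | 67-77% | 51-61% |

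The likelihood-ratio test of bTM at 0.05 rejects in 5-8% of these trials. Repeating the exercise with other sets of assumed shapes gives 30-49%, 49-67% and 67-77% for the observed range, with the Wald test rejecting in 3-5%.

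A hand check agrees. With no treatment effect, CD27 centred and normal, the estimates of bT and bTM have mean 0 and about equal standard errors, so their ratio is approximately Cauchy. Taking the observed range as about ±2.5 SD, the chance of crossing is (2/π)·arctan(2.5) = 0.76. For the 10th-90th percentiles (±1.28 SD) it is (2/π)·arctan(1.28) = 0.58. The standard error cancels from the ratio, so at a given CD27 range a larger trial would not lower this rate.

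**True interaction, 0.6 per SD, either sign.** At 25% v 45% the treatment log-odds ratio at the CD27 mean is logit(0.45) - logit(0.25) = -0.201 + 1.099 = 0.898. The true crossing is then 0.898/0.6 = 1.50 SD from the mean.
- Where that lies inside the data, the curves cross in 56-73% of trials, 1.5-2.0 times the no-interaction rate for the same shape. At 25% v 35% it is 68-83%, or 1.2-1.4 times.
- Where it lies outside the data (25% v 45%, three of the shape-and-sign combinations), the interaction is real but the curves do not cross in 52-65% of trials.

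**Precision of the cut-off** (25% v 45%, true crossing inside the data). With 1.0 per SD and a normal CD27, the true crossing is at -0.898 SD, the 18th percentile. Among trials that cross, the middle 90% of estimates runs from the 2nd to the 48th percentile. Over all shapes this span is 31-52 percentile points. The median bootstrap 95% interval is 52-100 points wide (52-65 in seven of nine scenarios, 95 and 100 in the other two). At 0.6 per SD it is 79-100 points.

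**Matched comparison.** If the likelihood-ratio cut-off is loosened so that its false-positive rate equals the crossing rate of the same shape, it detects 0.6 per SD in 56-74% of trials, against 56-73% for crossing (25% v 45%, true crossing inside the data).

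**The case against.** The text is hedged throughout, 13.5 places CD27 among exploratory endpoints, and no formal decision follows from a crossing. Thresholds are carried forward only if shown to predict outcome best, which is a further, though undefined, condition. The method is taken from a cited paper that may itself supply bands and intervals. A crossing in the extreme tail gives no useful split, so the 10th-90th percentile rates are the fairer figures. The futility rule and the p < 0.15 requirement in 13.1.3 also filter trials. With no effect, 44-46% stop early and 9-10% are recommended, and 3-5% of all trials are both recommended and show a crossing. Finally, crossing marks where the better arm changes, which is what a treatment-selection threshold needs, and at a matched error rate the interaction test detects no more.

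Much of this stands. The matter is modest, the gain is not better detection, and the cited paper cannot be checked here, so the point covers only what the two sections state. Three things do not follow:
- The central rates, 15-61%, are still well above 5%.
- The gates do not restrict the CD27 analysis, and a trial that misses its primary endpoint can still report a subgroup.
- Hedged wording conveys neither an error rate nor an interval. The curves and the crossing point can be kept, provided their uncertainty is shown with them.

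**Conclusion.** The concern holds, and the change should be made. As written, the criterion would flag a non-predictive CD27 in roughly a third to three quarters of trials, depending mainly on the true treatment effect. It would miss a real interaction without crossing in more than half of trials at 25% v 45%. The crossing point would often be uncertain over half or more of the CD27 range. Crossing does carry some information, since it is more frequent when an interaction exists and the true crossing lies inside the data.

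The percentages rest on assumed CD27 distributions, assumed arm rates and complete CD27 data; missing tissue would widen the uncertainty. The ordering is stable across every shape tried: chance crossing rises as the treatment effect shrinks and is always far above the rejection rate of an interaction test at 0.05.

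**What to change.** In 9.2.1.4 and in the CD27 paragraph of 13.5:
- Write the model as treatment + CD27 + treatment × CD27.
- Judge predictive potential by the interaction estimate with its confidence interval instead of by whether the curves cross. Report the test, but do not make 0.05 a mandatory gate.
- Plot both curves with bootstrap bands.
- Report any crossing-point threshold only with a bootstrap interval, and label it hypothesis-generating.

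The cost is wording in two places and minor code, with no new patients or specimens. The authors should expect wide intervals. Power for an interaction of 0.6 per SD at two-sided 0.05 is only about 10-29%, depending on CD27 shape, sign and test. With no interaction, the median 95% interval is about ±0.9 to ±1.4 log-odds per SD. A threshold will usually not be established. What the change buys is a stated error rate and an interval.

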9.3 Exploratory/Ancillary Correlative Studies

- 9.3.1 Comprehensive Analysis of Peripheral Blood Immune Cells by Mass Cytometry (CyTOF)
- 9.3.1.1 Collection of Specimen(s): 12 mL peripheral blood collected in yellow top tubes (ACD).

- 9.3.1.2 Handling and Shipping of Specimens(s): Kits will be provided for the collection of blood samples. The kit contains supplies and instructions for collecting, processing, and shipping specimens. Refer to Appendix E for kit ordering, sample collection, and sample shipping instructions.
- 9.3.1.3 Methodology: CyTOF (cytometry at time-of-flight) or mass cytometry is a new platform that uses mass spectrometry to allow evaluation of at over 35 simultaneous parameters on a single-cell level. This technology uses nonradioactive non-biological metal isotopes as reporters tagged to monoclonal antibodies. Measurements are made based on mass spectrometry, which largely avoids the hurdles of interference and spectral overlap experienced with fluorochrome-based flow cytometry. This constitutes an ideal platform for the study of the tumor microenvironment or immune monitoring given its ability to assess a large number of parameters and resolve small differences in a heterogeneous population of cells.

Mononuclear cells will be isolated from patient's peripheral blood via gradient separation using a Ficoll sodium diatrizoate solution (Ficoll-PaqueTM PLUS, GE Healthcare). The resulting mononuclear single-cell suspension will be suspended in freezing media containing 10% dimethyl sulfoxide and stored in liquid nitrogen or - 150°C freezer for analysis. Specimens will be stained in batches of 3-4 patients. Unstimulated live single-cell suspensions will be stained with a cocktail of metal-tagged antibodies designed to recognize 34 surface proteins (Appendix F). Nucleated cellular events will be identified using a DNA intercalator conjugated to natural abundance iridium (¹⁹¹Ir and ¹⁹³Ir). Cisplatin (¹⁹⁵Pt) will be used for dead-live cell discrimination and calibration beads containing natural abundance cerium (^{140/142}Ce), europium (^{151/153}Eu), holmium (¹⁶⁵Ho), and lutetium (^{175/176}Lu) will be used for normalization of acquired data. Our panel will be constructed using commercially available metal-conjugated antibodies (Fluidigm Corporation) and stained cells will acquired on the CyTOF2 (Fluidigm Corporation).

We will stain a minimum of 3 x 10^6 cells per specimen and acquire a minimum of 1 x 10^6 events on the CyTOF. We will initially perform high-level manual gating to exclude dead or apoptotic cells, debris, beads and doublets. Additional multiparametric analysis will be done using platforms such as Spanning-tree Progression Analysis of Density-normalized Events (SPADE) and visualization of unbiased clustering of events using the t-SNE (t-Distributed Stochastic Neighbor Embedding) algorithm or viSNE.

- 9.3.2 Identification/Characterization of Intratumoral Immune Cells by Immunohistochemistry (IHC) and CyTOF
- 9.3.2.1 Collection of Specimen(s): FFPE tumor tissue

9.3.2.2 Handling and Shipping of Specimens(s): FFPE tumor block(s) are preferred. Alternatively, a minimum of 13 unstained glass slides with 4-micron thick sections from FFPE per collection timepoint are acceptable. Please include a copy of the deidentified surgical pathology report, as well as study, site and patient study numbers. All FFPE specimens for correlative studies may be shipped together.

Shipping Procedure:

- 1. Place the block or slides in small zip-lock bag and seal.
- 2. Insert the bag containing the block or the slides in a bubble wrap bag.
- 3. Place wrapped samples inside the largest compartment of specimen biohazard bag and seal.
- 4. Insert a copy of the de-identified surgical pathology report in the outer pocket of the specimen biohazard bag.
- 5. Include a refrigerated cold pack (not frozen) if shipping in the summer months.
- 6. Place the specimen biohazard bag into the box and close.
- 7. Complete the transport documents and place into waybill pouch; affix to box.
- 8. Ship package to Mayo Clinic at the address below.
- 9. Please send email on the day of the shipment.

Please send FFPE tissue to:

Predolin Biobank Attn: [name] Mayo Clinic [name]

9.3.2.3 Methodology: Serial 4-µm paraffin-embedded sections will be used for IHC. The tissue will be deparaffinized with three changes of xylene and cleared through graded series of ethanol. Endogenous peroxidase will be quenched by incubation in 50% methanol/H2O2 and after rinsing with tap water; all sections will be pretreated for 30 minutes with 50 mmol/L EDTA using a steamer and cooled for additional 5 minutes. All staining will be done automatically on DAKO Autostainer using the following antibodies to CD11c (Leica Microsystems 5D11), CD14 (Cell Marque EPR 3653), CD163 (DAKO 1F8), CD68 (DAKO PG-M1), CXCL13 (R&D Systems 53610), FOXP3 (Abcam 236AE/7), CD3 (R&D Systems), PD-L1 (405.9A11), PD-L2 (366C.9E5), CD8a (Dako M7103) and PD-1 (Abcam NAT). The sections will be viewed with an Olympus BXFA51 microscope and pictures taken with an Olympus DP71 camera. Stained slides will be scored by expert hematopathologist. Internal control (reactive lymph node, tonsil) will be used to verify staining quality. Analysis of intra-tumoral immune cell subsets by IHC will be largely exploratory and reported descriptively.

For CyTOF analysis of intra-tumoral immune cells, we will perform multiparametric staining of single-cell suspensions obtained from FFPE blocks using the FFPE-

DISSECT (disaggregation for intracellular signaling in single epithelial cells from tissue) method. Single cells will be stained with the same 34-parameter surface protein panel (Appendix F). Nucleated cellular events will be identified using a DNA intercalator conjugated to natural abundance iridium (¹⁹¹Ir and ¹⁹³Ir). Cisplatin (¹⁹⁵Pt) will be used for dead-live cell discrimination and calibration beads containing natural abundance cerium (^{140/142}Ce), europium (^{151/153}Eu), holmium (¹⁶⁵Ho), and lutetium (^{175/176}Lu) will be used for normalization of acquired data. Our panel will be constructed using commercially available metal-conjugated antibodies (Fluidigm Corporation) and stained cells will acquired on the CyTOF2 (Fluidigm Corporation).

We will stain a minimum of $3 \ge 10^6$ cells per specimen and acquire a minimum of $1 \ge 10^6$ events on the CyTOF. We will initially perform high-level manual gating to exclude dead or apoptotic cells, debris, beads and doublets. Additional multiparametric analysis will be done using platforms such as Spanning-tree Progression Analysis of Density-normalized Events (SPADE) and visualization of unbiased clustering of events using the t-SNE (t-Distributed Stochastic Neighbor Embedding) algorithm or viSNE.

- 9.3.3 Evaluation of Genetic Alterations in Chromosome 9p24.1 by FISH
- 9.3.3.1 Collection of Specimen(s): FFPE tumor tissue
- 9.3.3.2 Handling and Shipping of Specimens(s): FFPE tumor blocks are preferred. Alternatively, a minimum of 13 unstained glass slides with 4-micron thick sections from FFPE per collection timepoint are acceptable. Please include a copy of the deidentified surgical pathology report, as well as study, site and patient study numbers. All FFPE tissue for correlative studies may be shipped together.

Shipping Procedure:

- 1. Place the block or slides in small zip-lock bag and seal.
- 2. Insert the bag containing the block or the slides in a bubble wrap bag.
- 3. Place wrapped samples inside the largest compartment of specimen biohazard bag and seal.
- 4. Insert a copy of the de-identified surgical pathology report in the outer pocket of the specimen biohazard bag.
- 5. Include a refrigerated cold pack (not frozen) if shipping in the summer months.
- 6. Place the specimen biohazard bag into the box and close.
- 7. Complete the transport documents and place into waybill pouch; affix to box.
- 8. Ship package to Mayo Clinic at the address below.
- 9. Please send email on the day of the shipment.

Please send FFPE tissue to:

Predolin Biobank Attn: [name] Mayo Clinic [name]

- 9.3.3.3 Methodology: The bacterial artificial chromosome probes (CHORI; www.chori.org) RP11-599H2O, which maps to 9p24.1 and includes CD274 (encoding PD-L1, labeled with Spectrum Orange), and RP11-635N21, which also maps to 9p24.1 and includes PDCD1LG2 (encoding PD-L2, labeled with Spectrum Green), will be cohybridized. A control centromeric probe, Spectrum Aqua–labeled CEP9 (Abbott Molecular) that maps to 9p11-q11, will be hybridized according to the manufacturer's recommendations. Nuclei with a target:control probe ratio of at least 3:1 will be classified as amplified, those with a probe ratio of more than 1:1 but less than 3:1 will be classified as relative copy gain, and those with a probe ratio of 1:1 but with more than two copies of each probe will be classified as polysomic for chromosome 9p. Analysis of genetic alterations Involving chromosome 9p24.1 by FISH will be largely exploratory and reported descriptively.
- 9.3.4 Evaluation of Serum Cytokine Profile by ELISA
- 9.3.4.1 Collection of Specimen(s): 10 mL of peripheral blood collected in red top tubes (No anticoagulant)
- 9.3.4.2 Handling and Shipping of Specimens(s): Kits will be provided for the collection of blood samples. The kit contains supplies and instructions for collecting, processing, and shipping specimens. Refer to Appendix E for kit ordering, sample collection, and sample shipping instructions.
 - 9.3.4.3 Methodology: Serial serum samples will be collected every 14 days before infusion of study drugs for the first 12 weeks of the study. Samples will be subjected to multiplex ELISA (Invitrogen, Camarillo, CA) to measure 30 serum cytokines. Luminex-200 system version 1.7 will be used for reading plates and MasterPlex QT1.0 system (MiraiBio) will be used to analyze data. Cytokines will include epidermal growth factor (EGF), eotaxin, basic fibroblast growth factor (FGF-b), granulocyte macrophage colony stimulating factor (GM-CSF), hepatocyte growth factor (HGF), IFN-α, IFN-Υ, interleukin 1 receptor antagonist (IL-1RA), IL-1β,IL-2, IL-2R, IL-4, IL-5, IL-6, IL-7, IL-8, IL-10, IL-12, IL-13, IL-15, IL-17, IP10, MCP-1, MIG, MIP-1α (CCL3), MIP1β (CCL4), regulated on activation normal T-cell expressed and secreted (RANTES), TNF-α and vascular endothelial growth factor (VEGF). Internal control serum will be included in all assays to control for interassay variation. Analysis of the serum cytokine by multiplex ELISA will be largely exploratory and reported descriptively.

- 9.3.5 Evaluation of Pharmacokinetics and Immunogenicity of CDX-1127 (varlilumab) and Nivolumab
- 9.3.5.1 Collection of Specimen(s): 20 mL of peripheral blood collected in red top tubes (No anticoagulant)
- 9.3.5.2 Handling and Shipping of Specimens(s): Kits will be provided for the collection of blood samples. The kit contains supplies and instructions for collecting, processing, and shipping specimens. Refer to Appendix E for kit ordering, sample collection, and sample shipping instructions.
- 9.3.5.3 Methodology: The pharmacokinetic properties and the ability of the study drugs to elicit an immunogenic response will be evaluated using standardized assays performed at their respective companies for the two study drugs. Blood draws will be obtained at baseline, pre-dose prior to the administration of drugs for the first 4 cycles, at end of treatment, and at the time of safety follow-up (if available) for all patients. Patients randomized to Group 1 who cross-over to Group 2 will need 4 additional blood draws to evaluate for immunogenicity to CDX-1127 (varlilumab) obtained pre-dose prior to the administration of the 4 initial doses of that medication.
- 9.3.6 Evaluation of Mutational Burden as a Biomarker for Response to Checkpoint Blockade Therapy
- 9.3.6.1 Collection of Specimen(s): FFPE tumor tissue
- 9.3.6.2 Handling and Shipping of Specimens(s): FFPE tumor blocks are preferred. Alternatively, a minimum of 13 unstained glass slides with 4-micron thick sections from FFPE per collection timepoint are acceptable. Please include a copy of the deidentified surgical pathology report, as well as study, site and patient study numbers. All FFPE tissue for correlative studies may be shipped together.

Shipping Procedure:

- 1. Place the block or slides in small zip-lock bag and seal.
- 2. Insert the bag containing the block or the slides in a bubble wrap bag.
- 3. Place wrapped samples inside the largest compartment of specimen biohazard bag and seal.
- 4. Insert a copy of the de-identified surgical pathology report in the outer pocket of the specimen biohazard bag.
- 5. Include a refrigerated cold pack (not frozen) if shipping in the summer months.
- 6. Place the specimen biohazard bag into the box and close.
- 7. Complete the transport documents and place into waybill pouch; affix to box.
- 8. Ship package to Mayo Clinic at the address below.

9. Please send email on the day of the shipment.

Please send FFPE tissue to:

Predolin Biobank Attn: [name] Mayo Clinic [name]

9.3.6.3 Methodology: Genomic DNA will be extracted from formalin-fixed, paraffinembedded (FFPE) tissue blocks or slides. Hematoxylin and eosin (H&E) stained sections from each case will be reviewed by an expert hematopathologist and representative blocks with at least 30% tumor cells will be selected. Sections of 10 x 4-micron dimensions will be cut from blocks (based on tissue area of 25 mm²). DNA will be extracted using the Qiagen FFPE DNA extraction kit. DNA quantitation will be performed using a Qubit fluorometer prior to sequencing. Whole exome analysis of paired tumor and normal tissue will be performed using Ion TorrentTM platform at the Molecular Characterization and Clinical Assay Development Laboratory, Leidos Biomedical Research Inc., Frederick National Laboratory for Cancer Research. The analysis of mutational burden by whole exome sequencing is largely exploratory and reported descriptively

